- Final Assessment/Discontinuation of documentation

Survival Sheets

After two documented Pfizer therapy sequences for advanced RCC, or if the treatment of advanced RCC, mantle cell lymphoma or gastrointestinal stromal tumor is terminated, the documentation changes to the "survival sheets".

The query will be initiated for the first time 12 months after the final visit, then every 6 months thereafter. For this purpose, a separate case report form will be provided to you by Winicker Norimed.

[figure not shown]
The patient interview in the indication area will be conducted during therapy with temsirolimus, sunitinib and axitinib at each visit.

For the indications mantle cell lymphoma and gastrointestinal stromal tumors, only

the documentation for temsirolimus and sunitinib should be used:

- Enrollment Visit
- Follow-up documentation (as per local guidelines, generally every 8-12 weeks)
- Final Assessment/Discontinuation of documentation
- 1-year follow-up for patients who discontinue therapy: Survival form (every 6 months thereafter)

Safety Criteria

In contrast to the usual procedure in clinical trials, patients will not be selected at the start of treatment (baseline) for this register. According to Amendment VI, this investigation may provide new information on the safety of sunitinib, temsirolimus, and axitinib following sunitinib and other therapeutic options.

It is intended to document any intolerances that the physician observes during the observation period related to the documented medicinal products. Additionally, adverse events (AEs) and serious adverse events (SAEs) will be collected, as defined below.

In addition, the physician's subjective assessment of tolerability of the therapy will be obtained at each visit.

Efficacy Criteria

The efficacy of treatment with temsirolimus, sunitinib and axitinib will be assessed during routine treatment evaluation and documented at each visit based on the following tools (examinations):

[figure not shown]
- Computed tomography (if available) and/or
- Magnetic resonance imaging (MRI) (if available)
- Ultrasound examination (if available)
- Chest X-ray (if available)

The following criteria will be used to assess efficacy:

- Survival time (OS)
- Progression-free time (PFS)
- Physician's assessment of therapy response (CR, PR, SD, PD)
- Physician's assessment of efficacy and tolerability of the therapy

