The biometric evaluation of the patient data (including statistical analysis plan) takes place, appropriate to the design of a registry, in a purely descriptive manner, and will be performed by a Contract Research Organization (Winicker Norimed GmbH, Nuremberg). An annual interim analysis will be performed.

Definition of analysis set

All prospectively documented patients with a histologically confirmed diagnosis of renal cell carcinoma, MCL, and GIST will be included in the "safety population".

All patients to whom at least one of the following criteria apply will be included in the "efficacy population": Date of death, time of progression, physician's assessment of therapy response, or therapy assessment of efficacy and tolerability by the physician are available.

Retrospectively documented information will not be included in the analysis.

Analysis of Safety Criteria

The absolute and relative frequency of patients with adverse events will be shown in a tabular form, both globally and according to the system organ classes and the MedDRA "preferred terms". In addition, the absolute and relative frequency of therapy dropouts will be presented both overall and according to discontinuation reasons. Serious adverse events will be evaluated separately. Previous and concomitant therapies will also be tabulated.

Laboratory analysis and electrocardiogram results will be analyzed per visit. In addition, the physician will assess information on tolerability during therapy.

Analysis of Efficacy Criteria

The change in disease activity will be described using the following parameters:

[figure not shown]
- Assessment of response to therapy by the physician
- Physician's assessment of efficacy
- Overall survival (OS)
- Progression-free survival (PFS)
- Maximum Response

For the analysis in STAR-TOR, the duration of treatment is defined as the period between inclusion in the registry and occurrence of any of the events of either death or discontinuation of the documentation or termination of therapy.

The duration of treatment will be evaluated using methods from the field of "survival time analysis".

Other analysis parameters

Comorbidities will be coded in accordance with MedDRA and concomitant medications according to WHO-DD. Frequencies for appropriate coding levels will be presented. Evaluation of sequence and therapy regimens and quality of life (advanced RCC) will be performed.

Case number estimate

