5.1 EFFECTIVENESS ANALYSIS SET

The effectiveness analysis set consists of all patients included into the study with at least one information on any of the following criteria: date of death, date of progression, assessment of response to therapy by the treating physician or an assessment to either effectiveness or tolerability of the therapy by the treating physician. For reporting the full analysis set will be labeled EAS.

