In case an event (either death or progression) was present and date of event was documented, the following definitions was used:

Overall Survival (OS, months) = $\frac{\text{date of death} - \text{date of baseline visit} +1}{365.25 *12}$

Progression Free Survival (PFS, months) = (minimum of (date of death, date of progression) – date of baseline visit + 1)/365.25 * 12.

In case information on dates were partly or completely missing or contradictory, the following was done:

• PFS:

- o the presence of a progression was confirmed, but no date was documented: if date of last intake of study medication was given, this date was used as date of progression, otherwise the date of the last visit with a documented "non-progression (e.g. SD)" was used as date of progression.
- o the presence of a progression was confirmed, but dates within a visit and on final documentation were contradictory, the prior date was used.
- o in case a death was documented within a survival follow-up/ within sequence 2 for subjects from sequence 1, but no progression was documented within regular study, the date of last visit + 1 day was used as date of progression.
- o in case no progression was documented, subject was censored with the latest available contact date / assessment date within study/within sequence.
- o in case these rules led to a missing duration or a negative duration, duration was set to "1 day".

• OS:

- o in case a death was documented, but date of death was unknown, the date of death was substituted with the latest available date for the patient (last visit, last contact date, date of assessment)
- o in case no death was documented, subject was censored with the latest available contact date / assessment date within study.
- o in case these rules led to a missing duration or a negative duration, duration was set to maximum of (PFS,"1 day").

Response to therapy (Recist criteria/ Cheson criteria)

Response to therapy according to the Recist/ Cheson criteria will be analyzed using the physician's assessment as documented in the CRF. As neither "size of lesion", "new lesions" or "increase in size" are defined as key fields, contradictory answers will not overvote physicians assessment.

"Best response" will be analyzed using the physician's assessment at final visit. If "Best response" is missing it will be determined from the best response documented during previous follow-up visits.

Treatment

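### Patients with no physician rating enter the effectiveness set only if they have an event, which can bias OS downward

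*SAP*

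**What the plan says.** SAP 5.1 requires "at least one information on any of the following criteria: date of death, date of progression", and continues with two further routes: "assessment of response to therapy by the treating physician or an assessment to either effectiveness or tolerability of the therapy by the treating physician". One item is enough. Protocol section 11 (definition of analysis set) has the same rule: "Date of death, time of progression, physician's assessment of therapy response, or therapy assessment of efficacy and tolerability by the physician are available".

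Ratings are planned as routine. Protocol section 11 states that "the physician's subjective assessment of tolerability of the therapy will be obtained at each visit". The flow charts place response and tolerability at follow-up visits, not at enrolment, and place the physician's overall response assessment on the completion/discontinuation form.

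Survival sheets come afterwards: "The query will be initiated for the first time 12 months after the final visit, then every 6 months thereafter". The flow charts mark no response, efficacy or tolerability item on them.

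For OS, SAP Appendix 1 (A1.3) says "in case no death was documented, subject was censored with the latest available contact date" or assessment date. SAP 8.2.3 and the 2.2 and 2.3 table series assign OS and PFS to the EAS only. SAP 5.3 defines no other set. Table 1.1-6.1 reports the size of the EAS and safety sets and the reasons for exclusion.

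**The concern.** Take a treated patient who has no rating of any kind. If a survival sheet reports death, the patient joins the EAS and counts as an OS event. If the same sheet reports the patient alive, no entry criterion is met, and that survival time is lost. The censoring rule in A1.3 would use the contact date, but the set definition stops the rule from reaching this patient.

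Inclusion in this subgroup therefore depends on the quantity being estimated, and the selection works in one direction only. The registry is descriptive, so the Kaplan-Meier medians are themselves the effectiveness result, and no OS analysis in all treated patients is planned that would reveal a shift.

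**Working it through.** The plan gives no figure to reproduce. The inputs below are assumptions, because the documents give neither the unrated share nor the contact rate.

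**Inputs.** Exponential OS with median 18 months (λ = ln 2 / 18 = 0.0385 per month); follow-up uniform from 3 to 60 months; share u with no rating; share c of those later contacted, so that death or survival is known. Missing ratings are taken as unrelated to prognosis. Unrated patients who are not contacted contribute nothing.

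**Share excluded.** Under these inputs 63.9% of patients die within follow-up and 36.1% are alive at its end. With c = 1 the excluded survivors are 0.361u of the cohort: 1.8%, 3.6% and 5.4% for u = 5%, 10% and 15%. Each has about 22 months of follow-up on average.

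**Effect on the hazard.** Every known death stays in the EAS, but unrated survivors are missing from the risk set. At time t the EAS hazard equals the true hazard times

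(1 − u + cu) / [(1 − u) + cu·r(t)],

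where r(t) is the probability that a patient still under follow-up at t dies before follow-up ends. Here r(0) = 0.639 and r(17) is about 0.51.

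- u = 10%, c = 1: 1/(0.9 + 0.1 × 0.639) = 1.037 at baseline and 1/(0.9 + 0.1 × 0.51) = 1.052 at 17 months. The average is about 1.045, and 18/1.045 = 17.2 months.
- u = 10%, c = 0.5: 0.95/(0.9 + 0.05 × 0.639) = 1.019 and 0.95/(0.9 + 0.05 × 0.51) = 1.026. The average is about 1.023, and 18/1.023 = 17.6 months.
- u = 10%, c = 0: 0.9/0.9 = 1. No change.

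Numerical integration of the same expression gives these EAS medians (true value 18.0 months):

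| Unrated | All contacted | Half contacted | None contacted |
|---|---|---|---|
| 5% | 17.6 | 17.8 | 18.0 |
| 10% | 17.2 | 17.6 | 18.0 |
| 15% | 16.8 | 17.4 | 18.0 |

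**Other settings.** Simulations with 10% unrated, all contacted: a true median of 12 months falls by 2.4% with follow-up of 12 to 60 months and by 6.0% with 6 to 24 months. A true median of 24 months falls by 5.1% with follow-up of 12 to 60 months. The effect is larger when follow-up is short, as at the interim analyses.

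**Limit of any change of set.** If deaths of unrated patients become known but their survivors are lost at baseline, the EAS and the full cohort give the same too-low median (11.7 against a true 12.0 months at 10% unrated). Adding patients censored at baseline changes nothing.

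**PFS.** With a true median of 6.0 months and 10% unrated, the EAS gives 5.3 months, and all enrolled patients under the same A1.3 rules give 5.5. Most of the loss therefore comes from a separate rule, which dates progression at the last visit plus one day when a death is found later without a documented progression.

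**The case against.** A reader who stops after the first two criteria might infer that the EAS leaves out patients known to be alive or progression-free, so that OS and PFS are both biased downward. The documents do not support that. A rating of CR, PR or SD is itself an entry criterion, as is one tolerability rating at any follow-up visit. Patients who leave early should still have the overall response assessment on the discontinuation form, and under the protocol the survival sheets start only 12 months after the final visit. (The SAP 2.1 text counts 12 months from baseline, while its flow chart counts from discontinuation.) Patients who withdraw consent to data collection supply no later follow-up (protocol 9.2). The affected group is therefore limited to patients with no follow-up rating, no final-form rating, and later contact.

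The shift is also small beside sampling error: with an assumed 400 patients, the standard deviation of the median in the 18-month setting is about 1.4 months. The registry has no hypotheses or decision rules, and Table 1.1-6.1 would show how many patients were excluded.

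All of this limits the size of the problem and stands. It does not remove it: the exclusion count does not give OS with those patients included, and a systematic shift does not shrink as the registry grows.

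**Conclusion.** The point holds for OS, in a narrow group. For patients with no physician rating, entry to the EAS depends on having an event, and OS can be biased downward. In the 18-month setting the loss at 10% unrated is about 0.8 months with full contact, about 0.4 with half contacted, and nil with none contacted. These figures rest on assumed unrated and contact shares and on missing ratings being unrelated to prognosis.

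It would go too far to say that OS and PFS are biased downward as a matter of fact, since the effect may be nil. For PFS, the set definition is the smaller of two sources, behind the dating rule in A1.3.

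**What to change.** Analyse OS in the safety analysis set of SAP 5.2, which is defined without reference to outcome, and censor patients without a documented death at last contact. Align the protocol's definition of the efficacy population, and report how many safety-set patients have no rating and how many of those have later contact. Keep the EAS for response and physician-assessment tables. If the primary set is not changed, add this OS analysis as a sensitivity analysis.

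Do not simply delete the death and progression routes. A set that required a rating at 8 to 12 weeks would drop early deaths and raise a true median of 12.0 months to 14.3.

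If PFS is also run in the safety set, censor patients without an event at the last tumour assessment or treatment-phase visit. Survival sheets carry no tumour assessment, so censoring at a sheet contact would count never-assessed patients as progression-free. With a median PFS of 6 months, a median of 12 months from progression to death and 10% unrated, that would more than double 36-month PFS, from 2^(−36/6) = 1.6% to about 3.4%.

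The cost is a wording change in both documents and a different set flag for OS. Patients with baseline data only are added but carry almost no information.

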5.2 SAFETY ANALYSIS SET

The safety analysis set consists of all prospectively documented patients included in the study with a histologically proven diagnosis of either renal cell carcinoma, MCL or GIST and at least one documented administration of temsirolimus, sunitinib or axitinib or any non-Pfizer treatment.

5.3 OTHER ANALYSIS SET

Not applicable.

5.4 SUBGROUPS

Effectiveness analyses of mRCC patients will be repeated for subgroups based on physician's prognosis of patients risk and for the risk groups according to Motzer score, modified Motzer score and Motzer score for pretreated patients.

For subjects in first line Torisel[®] therapy with poor prognosis according to modified Motzer the following variables will be analyzed: age, gender, Karnofsky index, organs with metastases, prior surgeries, duration of disease, histology, progression free survival and overall survival.

Effectiveness analyses of MCL patients will be repeated for subgroups based on the risk groups according to MIPI (Mantle cell lymphoma international prognostic index).

Effectiveness analyses of GIST patients will be repeated for subgroups based on physician's prognosis of patients risk and for the risk groups according to Fletcher Risk Table.

[figure not shown]
6 ENDPOINTS AND COVARIATES

6.1 EFFICACY/EFFECTIVENESS ENDPOINT(S)

Variable	Role	Operational definition		
Overall survival	Outcome	presented in months		
Progression free survival	Outcome	presented in months		
Response to therapy	Outcome	according to RECIST / according to Cheson (for MCL)		
Physician's global assessment	Outcome			
Karnofsky performance status	Outcome Subgroup identifier	not for MCL		
ECOG performance score Outcome Subgroup identifier		only for MCL		

6.2 SAFETY ENDPOINTS

Variable	Role	Operational definition
Incidence and severity of treatment-emergent adverse events	Safety outcome	
Discontinuation due to adverse event	Safety outcome	
Discontinuation from Study	Safety outcome	
Serious adverse events	Safety outcome	
Death	Safety outcome	either "intensity according to NCI-CTC-criteria = grade V fatal" or "outcome = exitus" or "event term = death"
Laboratory values (if available)	Safety outcome Subgroup identifier	Hemoglobin, calcium, albumin, LDH, creatinine, ALT, AST, alkaline phosphatase, total bilirubin, TSH, fT3, fT4, hematocrit, phosphate, HbA1c, glucose, neutrophils, lymphocytes, monocytes, eosinophils, basophils, sodium, potassium, magnesium, cholesterol, triglycerides
Global tolerability assessment	Safety outcome	

PFIZER CONFIDENTIAL

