6.4.2 Mantle Cell Lymphoma International Prognostic Index (MIPI)

MIPI score is defined as

Score = $0.0353 * age (yrs) + 0.6978 * [ECOG > 1 {yes/no}] + 1.367*log₁₀(LDH/ULN LDH) + 0.9393*log10(Leukocyte count [/µl])$

Low risk if Score < 5.7

Intermediate risk if $5.7 \le \text{Score} < 6.2$

High risk if $6.2 \le Score$

If all data necessary to compute MIPI score are available, the calculated risk will be used for analyses of current MIPI. Otherwise and for the time of primary diagnosis the value documented by the physician will be used.

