8.2 STATISTICAL ANALYSES

8.2.1 Summary of Efficacy/ Effectiveness Analyses

Not applicable

8.2.2 Safety Analyses

Adverse events will be analyzed giving absolute and relative frequencies in total and by MedDRA system organ classes and preferred term. Serious adverse events will be analyzed separately in the same manner.

Adverse events will presented within each treatment (temsirolimus, sunitinib, axitinib) and for all non-Pfizer treatments in total and by treatment.

Additionally the absolute and relative frequency of patients with premature discontinuation will be presented in total and by reason for premature discontinuation.

Prior and concomitant medication will be presented showing frequency tables.

Laboratory results and ECG results will be presented by visit.

Physician's assessment of tolerability will be analyzed presenting sample statistics.

8.2.3 **Summary of Analyses**

Outcome	Analysis Set	Supports Protocol Objective Number	Subgroups	Statistical Method	Covariates/ Strata	Missing Data
Demographic characteristics: age, height, weight, BMI, sex	Safety, EAS	4	None	Sample statistics	None	Excluded
Incidence of treatment- emergent adverse events	Safety	3	Patients receiving CYP3A4 inducing concomitant medication (only patients treated with temsirolimus) Patients receiving CYP3A4 inhibiting concomitant medication (only patients treated with temsirolimus)	Rate by SOC and PT	Non-serious AE, serious AE	Excluded
Discontinuations due to AE	Safety	3	None	Rate by SOC and PT	None	Excluded
Discontinuation from Study	Safety	3	None	Rate for reason for discontinuation	None	Excluded
Serious Adverse Events	Safety	3	None	Rate by SOC and PT	None	Excluded
Deaths	Safety	3	None	Rates for reason for deathListing of deaths	None	Excluded
Laboratory values	Safey	3	None	Sample statistics by parameter and visit	None	Excluded

Outcome	Analysis Set	Supports Protocol Objective Number	Subgroups	Statistical Method	Covariates/ Strata	Missing Data
Global tolerability assessment	Safety	2	None	Frequency table	None	Excluded
Overall survival	EAS	1	- 1 st line patients	Kaplan-Meier estimates; Kaplan- Meier curves; Log-rank test	 indication mRCC, GIST, MCL risk prognosis line of treatment low vs. high LDH response to prior therapy age groups (≤65 yrs; > 65 yrs) 	

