				.1 total .2 by treatment sequence .3 by line
3.1-1.2	Summary of adverse events by concomitant CYP3A4 inducing or inhibiting medications	Torisel® mRCC / MCL	Safety	repeat table 3.1-1.1 by subgroups according to CYP3A4 inducing or inhibiting medication (if number of patients with these medications is sufficiently large
3.1-2	All adverse events (by patients)	All	Safety	Incidence rates overall and for Primary System Organ Classes (PSOC) and preferred terms of MedDRA (non-serious/serious as columns) 1 total 2 by treatment sequence 3 by line
3.1-3	AE by severity (NCI-CTC grade)	All	Safety	Incidence rates overall and for PSOC and preferred terms of MedDRA severity: max. NCI-CTC grade within patient, PSOC, preferred term resp.(non-serious/serious as columns)
3.1-4	AE with relationship to study drug	All	Safety	Incidence rates overall and for PSOC and preferred terms of MedDRA (non-serious/serious as columns)
3.1-5	AE with action taken "Study medication permanently discontinued"	All	Safety	Incidence rates overall and for PSOC and preferred terms of MedDRA (non-serious/serious as columns)
3.1-6	AE by outcome (event basis)	All	Safety	Number of events overall and for PSOC and preferred terms of MedDRA
3.1-7	Treatment emergent AE: action taken (event basis)	All	Safety	Number of events overall and for PSOC and preferred terms of MedDRA
3.2	Deaths, other serious and significant adverse events			
3.2-1.1	Listing of deaths	All	Safety	Sorted by patient
3.2-1.2	Reason for death	All	Safety	Frequency table
3.2-1.3	Listing of serious adverse events (SAE, except deaths)	All	Safety	Sorted by patient

Table No.	Title	Treatment/ Indication	Analysis set	Description
3.2-1.4	Listing of SAE with outcome study treatment permanently discontinued	All	Safety	Sorted by patient
3.3	Laboratory values			
3.3-1	Hematology			
3.3-1	Laboratory values: hematology – study course	All	Safety	.x per parameter Sample statistics by visit, including difference and relative changes to baseline
3.3-2	Clinical chemistry			
3.3-2	Laboratory values: clinical chemistry- study course	All	Safety	.x per parameter Sample statistics by visit, including difference and relative changes to baseline
3.4	Global tolerability assessment			
3.4	Physician's global tolerability assessment	All	Safety	Frequency table by time windows and for the last documented visit
3.5	Vital signs, ECG, echocardiography and pain			
3.5-1	Course of blood pressure	mRCC	Safety	Sample statistics by time windows

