EQ-5D-TTO will be calculated from EQ-5D raw values according to the following formula (Greiner, W. et al. 2005):

EQ-5D-TTO = 0.999

- 0.099 * (1*Subject has some problems with walking around + 2 * Subject cannot walk around)

- 0.087 * (1*Subject has some problems with self-care + 2 * Subject has extreme problems with self-care)

- 0.112 * (1*Subject states moderate pain or discomfort + 2 * Subject has extreme pain or discomfort)

- 0.129 * (Subject cannot walk around)

- 0.091 * (Subject has extreme pain or discomfort)

- 0.065 * (Subject is extremely anxious or depressive)

- 0.323 * (Subject states major problems in at least one dimension).

EQ-5D-TTO-values range from -0.205 to 0.999.

Laboratory values

Additional queries were written in the following cases:

- calcium > 10 mmol/L
- albumin > 100 g/L
- hemoglobin > 20 g/dL
- LDH < 80 U/L or > 1000 U/L
- albumin in % of total protein.

Laboratory values were set to "missing" if the documented values were outside the ranges given in the following table:

Laboratory parameter	Lower plausibility range	Upper plausibility range
Neutrophils	6%	100%
Lymphocytes	2.5%	85%
Monocytes	-	26%
Eosinophils	-	16%
Basophils	-	5%
Leukocytes	-	28 G/L
Platelets	-	1000 G/L
Hemoglobin*	-	20 g/dL
Creatinine	-	12 mg/dL
Calcium*	-	10 mmol/L
Sodium	-	320 mmol/L
Potassium	-	15 mmol/L
Phosphate	-	4 mmol/L
Magnesium	-	7 mmol/L
ALT (GPT)	1 U/L	1400 U/L

Laboratory parameter	Lower plausibility range	Upper plausibility range
AST (GOT)	1 U/L	1400 U/L
Gamma-GT	1 U/L	1400 U/L
Alkaline Phosphatase	1 U/L	5100 U/L
Total bilirubin	-	25 mg/dL
Albumin	-	100 g/L
LDH*	80 U/L	1000 U/L
Cholesterol	-	26 mmol/L
Triglycerides	-	35 mmol/L
HbA1c	1%	10%
Glucose	-	_**
TSH	-	21 mU/L
beta-2 Microglobulin	-	-

^{*:} Risk factors according to Motzer score will be set prior to check on plausibility.

CYP3A4-inducing and inhibiting substances

A combination of Torisel® and CYP3A4 influencing substances should be handled carefully. Thus documented concomitant medication will be checked manually for CYP3A4 inducing and inhibiting substances by the medical expert.

If the number of patients who received either CYP3A4 inducing or inhibiting substances is sufficiently large, parts of the safety analysis will be repeated for those subgroups.

Comorbidities

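### SAP 6.2 leaves leukocytes and platelets off the named laboratory safety outcomes, and no absolute neutrophil or lymphocyte count is derived, so the reporting of falls in these counts is not assured

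*SAP*

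**What the plan says.** SAP 6.2 defines the laboratory safety outcome by a list of named parameters, collected where available. It opens with "Hemoglobin, calcium, albumin, LDH, creatinine, ALT, AST, alkaline phosphatase, total bilirubin, TSH, fT3, fT4, hematocrit" and runs on, from hematocrit, with "hematocrit, phosphate, HbA1c, glucose, neutrophils, lymphocytes, monocytes, eosinophils, basophils, sodium, potassium, magnesium, cholesterol, triglycerides". Nothing marks the list as open-ended or as examples. The five white-cell types carry no unit.

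SAP Appendix 1, A1.3 (Laboratory values), gives a second list, a table of plausibility limits. Values are set to missing "if the documented values were outside the ranges given in the following table". This table includes leukocytes and platelets with limits in G/L, and gives the white-cell types limits in percent. Leukocytes also enter the MIPI formula in SAP 6.4.2, as "Leukocyte count" per microlitre.

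The output is Table 3.3-1 in SAP section 9, titled "Laboratory values: hematology – study course". It covers all treatments and indications in the safety set, with one sub-table per parameter and the content "Sample statistics by visit, including difference and relative changes to baseline". It names no parameters and does not refer to 6.2 or A1.3. The summary in SAP 8.2.3 adds only "Sample statistics by parameter and visit". The protocol (section 11, analysis of safety criteria) commits to a per-visit laboratory analysis without listing parameters.

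**The concern.** The safety profile of three anticancer drugs is a stated objective in both documents (protocol section 6, SAP 2.2). For such drugs a reader expects the hematology course to cover platelets, leukocytes and absolute neutrophils. The only named outcome list leaves out the first two, and the SAP gives no route to the third.

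A percentage is a share of a total. If the total moves and is not reported beside it, neither the percentage nor its relative change tells the reader what happened to the count. A table built strictly from 6.2 could look flat while counts fall, or show a rising neutrophil share because another cell type fell.

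**Working it through.** The plan gives no figure to reproduce here. The check is a comparison of the two lists, followed by arithmetic on assumed values.

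**1. The two lists.** SAP 6.2 has 26 parameters and the A1.3 table has 27; 23 are in both.
- Only in A1.3 (27 - 23 = 4): leukocytes, platelets, gamma-GT, beta-2 microglobulin.
- Only in 6.2 (26 - 23 = 3): fT3, fT4, hematocrit.

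| Parameter | Named in SAP 6.2 | A1.3 lower limit | A1.3 upper limit |
|---|---|---|---|
| Leukocytes | no | none | 28 G/L |
| Platelets | no | none | 1000 G/L |
| Neutrophils | yes, no unit | 6% | 100% |
| Lymphocytes | yes, no unit | 2.5% | 85% |

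So the SAP expects leukocytes and platelets in the data and screens them, and low values of either are kept. Platelets have no other use in the visible SAP.

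**2. What a percentage can hide.** Absolute count = leukocytes (G/L) x percent / 100. All values in this step are assumed, since the documents give none. With neutrophils at 60% throughout:
- leukocytes 6.0 G/L: 6.0 x 0.60 = 3.6 G/L
- leukocytes 3.0 G/L: 3.0 x 0.60 = 1.8 G/L (1.8/3.6 - 1 = -50%)
- leukocytes 1.5 G/L: 1.5 x 0.60 = 0.9 G/L (0.9/3.6 - 1 = -75%)
- leukocytes 0.8 G/L: 0.8 x 0.60 = 0.48 G/L (0.48/3.6 - 1 = -87%)

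The percentage changes by 0% in every case. More generally, if neutrophils change by a factor (1 + n) and leukocytes by (1 + w), the percentage changes by (1 + n)/(1 + w) - 1. This is zero whenever n = w, however large the fall. It is positive when neutrophils are unchanged (n = 0) and the total falls (w < 0).

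**3. Whether adding leukocytes alone would be enough.** It would show the fall in the example above. It would not give the distribution of absolute counts, because the mean over patients of leukocytes x percent is not in general the mean of leukocytes times the mean of percent. The product has to be formed per patient and visit.

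**4. Effect of the cleaning rule.** A neutrophil share below 6% is set to missing. At leukocytes of 6.0 G/L that removes counts below 6.0 x 0.06 = 0.36 G/L; at 1.5 G/L, below 1.5 x 0.06 = 0.09 G/L. The same rule removes lymphocyte shares below 2.5%. The asterisked exemption in A1.3 covers hemoglobin, calcium and LDH only, for setting Motzer risk factors, and the white-cell types are not on the A1.3 list of additional queries.

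**5. The adverse event route.** Protocol Table 1 requires all adverse events, serious or not, to be documented. Protocol section 10.2 (abnormal findings) makes a finding an adverse event if it is accompanied by symptoms, needs further diagnostic work or intervention, leads to dose modification or study termination with significant additional treatment, or is classed as one by the physician or sponsor. Recurring findings that meet none of these are excluded. Qualifying cytopenias therefore reach Tables 3.1-2 and 3.1-3 (preferred term, NCI-CTC grade); asymptomatic, unmanaged falls need not.

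**The case against.** The strongest reply is that the SAP excludes nothing. Table 3.3-1 is open, so a programmer could include every hematology parameter in the database, and screening platelets suggests an intention to summarise them. The two lists differ in both directions, which looks like loose upkeep as much as a decision to drop blood counts. Percent appears only as a cleaning limit; SAP 6.2 states no unit. The numerical example is assumed, and its fall would be visible if leukocytes were tabulated. Some of the SAP is also blacked out, so absence from the visible text is weaker evidence than usual.

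Most of this is fair, and it rules out two stronger readings that a reader might infer. One is that falls in platelets or absolute counts cannot appear in the laboratory tables; the open shell contradicts that. The other is that they would be seen only if a physician chose to report them; the protocol obliges documentation of findings that meet its criteria.

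What remains is that nothing requires these parameters to be reported, and the one list that names the outcomes leaves them out. A plausibility limit is a cleaning rule and does not commit anyone to a table. Even a programmer who adds leukocytes and platelets has no derivation for absolute neutrophils or lymphocytes.

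**Conclusion.** The point holds as a gap between the endpoint list and the plausibility table, with no statement of which governs Table 3.3-1. Reporting of leukocytes, platelets and absolute neutrophil and lymphocyte counts is not assured. If the tables follow 6.2 with percentages, a fall of 75% in absolute neutrophils can appear as no change.

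This rests on two assumptions: that the white-cell types are held as percentages, which the limits imply but no text states; and illustrative leukocyte values, so nothing can be said about how often such falls occur. Severity is low to moderate. The registry is purely descriptive, the SAP has no hypotheses or decision rules, and laboratory values are collected only where available. It is still more than a missing detail, because the adverse event tables do not cover asymptomatic, unmanaged falls and the remedy is cheap.

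**What to change.** - Add leukocytes and platelets to the list in SAP 6.2. Name the parameters of Table 3.3-1 there, with units, so that one list governs.
- In A1.3, derive absolute neutrophil and lymphocyte counts per patient and visit as leukocytes (G/L) x percent / 100. Summarise them, with change from baseline, next to the percentages.
- For neutrophils below 6% and lymphocytes below 2.5%, query the value or keep it for this derivation. Otherwise the rule deletes some of the lowest counts before they can be summarised.
- While the lists are open, settle the other mismatches: gamma-GT, beta-2 microglobulin, fT3, fT4 and hematocrit.

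The cost is SAP wording, a short derivation and a few more table pages, from values the SAP already screens. Queries add some site work; keeping the low values avoids it. No absolute count can be given where only one of the two values was documented, so each table should show the number of patients contributing.
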